## 6. INFORMED CONSENT FORM AND MEDICAL HISTORY FORM

An informed consent will be obtained from each subject consistent with requirements in 21 CFR 50 prior to initiating the study describing reasons for the study, possible adverse effects, associated risks and potential benefits of the treatment and their limits of liability. Subjects will sign and date the informed consent document to indicate their authorization to proceed and acknowledge their understanding of the contents. Each subject will be sent home with a signed and dated copy of the informed consent form. Each subject will be assigned a subject identification number

and medical history information will be collected. This information, along with the signed consent forms will be available for inspection on the premises of ALS only.

## 7. EXPERIMENTAL TECHNIQUES AND METHODS

This will be a single center, with no randomization or blinding, study design in 30 healthy adult subjects, age 18-70 years. Based on prior experience approximately 30 subjects will be enrolled to ensure 20 subjects complete the study.

Skin response to the test product and both positive and negative controls will be evaluated and measured by an allergist. If the measured diameter is  $\geq 3$ mm in response to the test product with expected reactions to both the positive and negative controls, the site will be considered a positive allergen.

Initial reading will take place after 15 minutes looking for the presence or absence of a wheal and flare at all three sites and measuring the diameter of both the wheal and flare if present. The wheal at the positive control must exceed a wheal at the negative control by 3 mm. A second reading is conducted about 6 hours after the SPT administration and similar measurements are taken. The subjects return to the office 1-2 days after the initial administration for a third test reading and measurements. A positive reaction is present when there is a measurable wheal of  $>3$  mm. Small wheals are confirmed by palpation. The skin prick reaction is quantified by measuring the mean diameter of the wheal, using a ruler marked in mm. If the result is a circular wheal, one measurement of the diameter (in mm) is sufficient; if ovoid or irregular, two diameters are measured (smallest and largest) and the numbers are added and divided by 2 (mean diameter). A flare alone is measured but is not of any clinical significance. The flare, area of erythema, may also be recorded by the same method.

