## 2. OBJECTIVE

To determine the sensitization (contact allergy) potential of test product ColActive Plus Collagen Matrix Dressing after a skin prick test to the skin of human subjects.

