## 8. BACKGROUND

Skin prick testing (SPT) is a standard method for diagnosing allergic sensitization. SPT interpretation utilizes the presence and degree of cutaneous reactivity as a surrogate marker for sensitization within target organs, i.e., eyes, nose, lung, gut, and skin. When relevant allergens are introduced into the skin, specific IgE bound to the surface receptors on mast cells are cross-linked, mast cells degranulate, and histamine and other mediators are released. This produces a wheal and flare response which can be quantitated. Many different allergens can be tested simultaneously because the resultant reaction to a specific allergen is localized to the immediate area of the SPT.

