## 11. ADVERSE EVENTS

The most commonly observed reactions in this study are:

1. Itching, redness, rash, peeling, swelling and in rare cases blistering.
2. There is also a possibility of a reaction from the tape, which may result in hyperpigmentation.

There also may be risks and discomforts, which are not yet known.

An adverse event (AE) is any unfavorable medical occurrence experienced by the subject, whether or not the event may be related to the test article.

Each adverse event must be promptly recorded and sufficiently documented by the Study Director in the source documentation and case report form even if the adverse event is assessed by the Study Director as unlikely to be related to the study. Adverse events are graded on a scale of severity (mild, moderate, severe, or life threatening) and

on a scale of relationship to the product (unknown, unrelated, unlikely, possible, probable, or definite). All adverse events will be reported to the Sponsor within five business days. All adverse events will be followed up until resolved, stabilized, the subject is lost to follow-up or the event is otherwise explained. All follow-up information should be reported to the Sponsor.

A serious adverse event (SAE) as defined in the CFR 312.32 is "any experience that is fatal or life threatening, is permanently disabling, requires inpatient hospitalization, or is a congenital anomaly, cancer, or overdose". All serious adverse events will be reported to the Sponsor within 24 hours of ALS Beauty & Personal Care notification.

If, according to the Investigator, medical care is warranted, appropriate referrals will be made. ALS Beauty & Personal Care will follow adverse events until resolution.

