## **14. STATISTICAL RATIONALE AND DATA REPORTING**

Evaluation of results consists of only one physiological measure (that of wheal/flare) measured at 3 time points: T1=15 minutes after SPT, T2=6hr after SPT and T3=24-48 hrs. after SPT. Our power analysis calculation indicates at a confidence level of 99% and confidence interval of 1.35, we will need a sample size of n=20. No statistical analysis will be performed. No significant effect or interaction effects are anticipated hence the small sample size. Skin responses to the test product and controls for each subject will be presented in a table in the final report.

Product reporting for skin sensitization will be based on statistically significant positive scores at each interval. Any subject that has erythema present in the negative control eliciting an allergic response will be included as long as the wheal diameter of the positive control exceeds the wheal size of the negative control by at least 3mm. This is to account for individuals who have sensitive skin. This data will be noted in the clinical findings.

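### At 6 and 24-48 hours only a wheal of about 3 mm can count, so other late reactions at the product site cannot inform the contact-allergy result

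*Combined protocol and SAP*

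**What the plan says.** Section 2 states the aim: "To determine the sensitization (contact allergy) potential of test product ColActive Plus Collagen Matrix Dressing after a skin prick test". Section 8 explains the test by one mechanism: "specific IgE bound to the surface receptors on mast cells are cross-linked, mast cells degranulate, and histamine and other mediators are released", which produces the wheal and flare.

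Section 7 schedules three readings. At 15 minutes, wheal and flare are looked for and measured at the product, positive-control and negative-control sites. Then: "A second reading is conducted about 6 hours after the SPT administration and similar measurements are taken". And: "The subjects return to the office 1-2 days after the initial administration for a third test reading and measurements". The positivity rule follows with no time point attached: "A positive reaction is present when there is a measurable wheal of" more than 3 mm. The reaction is quantified by mean wheal diameter. On erythema, the section says: "A flare alone is measured but is not of any clinical significance". Its next sentence makes recording the flare optional.

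Table 1 grades by wheal size, with pseudopods as the only other feature; below 3 mm is zero, or negative. Section 9.6 repeats the wheal rule (there as 3 mm or more). It has the allergist evaluate the sites at 6 and 24-48 hours without naming a different scale.

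Section 14 says: "Evaluation of results consists of only one physiological measure (that of wheal/flare) measured at 3 time points". It bases product reporting on positive scores at each interval and promises a table of each subject's responses to product and controls.

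Section 11 lists the reactions most commonly seen in the study: "Itching, redness, rash, peeling, swelling and in rare cases blistering".

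**The concern.** The two later readings use up a long first day and a return visit, so they should add something to the 15-minute wheal. As the plan stands, they add only a repeat search for a wheal. If the product site is red, papular or blistered at 48 hours but shows no wheal of the required size, it receives the lowest grade and contributes nothing to the product result.

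At stake is how a clean late result is read. With an objective phrased as contact allergy, a report of no positive scores at 6 and 24-48 hours invites the conclusion that no late reaction occurred. The score supports only the narrower statement that no late wheal occurred.

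**Working it through.** The plan states no figure on this point, so there is none to reproduce; the sample size of 20 in Section 14 does not bear on it. The check is to follow possible late findings at the product site through the rules.

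1. **Which rule applies late?** Section 7 describes all three readings and then gives one rule. Section 9.6 refers back to Section 7 and calls the later evaluations grading, but Table 1 is the only scale supplied. It is labelled a sample scale, yet nothing replaces it. The wheal rule therefore governs all three readings. One earlier sentence in Section 7 speaks of a measured diameter without naming the wheal; the later sentences, Table 1 and Section 9.6 settle that it is the wheal.

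2. **What happens to each late finding?**

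| Late finding at the product site | Field in the plan | Can it make the reading positive? |
|---|---|---|
| Wheal above 3 mm | Mean wheal diameter, Table 1 | Yes |
| Wheal under 3 mm | Mean wheal diameter, Table 1 | No |
| Erythema without a wheal | Flare diameter, recording optional on one wording | No |
| Vesicle, papule, rash or peeling without a wheal | None; adverse event form only | No |

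   A wheal of exactly 3 mm depends on which of the two wordings (more than 3 mm, or 3 mm and above) is used. They need reconciling, but the point does not turn on it.

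3. **Is erythema treated consistently?** No. Section 7 denies a flare alone any clinical significance, without limiting this to 15 minutes. Sections 9.6 and 14 discuss erythema at the negative control as an allergic response, tolerated if the positive-control wheal exceeds the negative-control wheal by at least 3 mm, and Section 14 has it noted in the clinical findings.

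4. **Is there another route to the product result?** Section 11 has adverse events recorded and graded for severity and relationship to the product. Neither it nor Section 14 carries them into the sensitization conclusion.

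5. **How many readings fall under the rule at late times?** Two of three per subject; with 20 completers, 20 × 2 = 40 of 20 × 3 = 60 product-site readings. This counts readings that could be affected, not readings graded wrongly. The latter would need the rate of late non-wheal reactions, which the documents do not give.

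**The case against.** The strongest reply is that a skin prick test is meant to read wheals, and that a wheal score which counts only wheals is doing its job. Scoring a late reaction without a wheal as negative is an error only if such a reaction signifies sensitization, and the documents nowhere say that it does. This stands, and it is why these reactions should be described separately and not counted as positives.

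Other parts of the defence also stand:

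- Redness is not simply lost. Flare is among the measurements at all three readings, and responses are tabulated by subject. What remains is the optional recording and the inability to affect the score.
- Swelling is not wholly outside the scale, since a wheal is a swelling and small wheals are already palpated.
- A blistered site would be recorded as an adverse event and reported to the sponsor. Section 10 also keeps data from subjects discontinued for product-related reasons. The missing piece is the link to the conclusion.
- The Section 11 list is weak evidence of what this test will produce. The same section warns of a reaction to tape, which the procedure does not use, so the list looks generic. It also does not call the reactions allergic.

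None of this supplies a late criterion, or a route from a non-wheal finding to the product result.

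**Conclusion.** The point holds as a gap in recording and reporting. At 6 and 24-48 hours, a product-site reaction without a wheal of about 3 mm cannot affect the product result, although the stated objective is contact allergy and the wheal is explained only as an IgE and mast-cell response. This rests on reading Section 7's rule as applying to all three visits, which the text supports and nothing contradicts.

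A reader might infer more: that true sensitization will be missed, that the 40 late readings are unreliable, or that some fraction of subjects will be misreported. The documents support none of these. They give no rate of late non-wheal reactions, so no magnitude can be derived, and they do not establish that such reactions are sensitization; they could be irritant or caused by the prick. The per-subject table remains usable. The risk is that its late negatives are over-read, and the remedy is cheap.

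**What to change.** - Keep the wheal score at all three readings.
- Make flare/erythema recording mandatory at 6 and 24-48 hours, removing the conflict in Section 7 between measuring it and optionally recording it.
- Add fields for induration or papule and for vesicle or blister at both late readings, at all three sites, completed by the allergist.
- Report, at each late reading, any non-wheal reaction at the product site that is absent or smaller at the negative control. Present it as a separate descriptive outcome, not as a positive score.
- Limit the sentence on flare alone to the 15-minute reading, and reconcile it with the erythema wording in Sections 9.6 and 14.
- Word the conclusion so that no wheal at the late readings is not reported as absence of contact allergy.

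The cost is a few columns on the grading form and one in the report table; visits, sites, assessor and sample size do not change. The drawback is that some non-specific redness from the prick or the vehicle will be recorded. The negative-control comparison only partly separates this, because the control is saline with glycerin while the product is prepared in distilled water.

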**Table 1**  
**Sample grading scale for skin-prick testing**

Grade	Wheal Size
0 or Negative	Less than 3 mm
+1	3 mm to 5 mm
+2	6 mm to 10 mm
+3	11 mm to 15 mm
+4	Greater than 15 mm or pseudopods

## 8. BACKGROUND

Skin prick testing (SPT) is a standard method for diagnosing allergic sensitization. SPT interpretation utilizes the presence and degree of cutaneous reactivity as a surrogate marker for sensitization within target organs, i.e., eyes, nose, lung, gut, and skin. When relevant allergens are introduced into the skin, specific IgE bound to the surface receptors on mast cells are cross-linked, mast cells degranulate, and histamine and other mediators are released. This produces a wheal and flare response which can be quantitated. Many different allergens can be tested simultaneously because the resultant reaction to a specific allergen is localized to the immediate area of the SPT.

## 9. PROCEDURE

### 9.1 Consent

Subjects will be given an informed consent form (ICF), inclusive of a HIPAA disclosure and California Subject Bill of Rights, to read and sign. They will have all of their study related questions answered by the Investigator or designated staff. Subjects who qualify based on the inclusion and exclusion criteria will be enrolled into the study.

*9.2 Method of Application:*

UniTest PC device through a drop of allergen extract. All applications will be to the volar forearm.

*9.3 Test Product/Equipment:*

The test product will be provided by the sponsor. Test product will be applied using a UniTest PC device to the test site (volar forearm). Aliquot all test articles into their respective sterile reservoir to serve as a basin during application.

*9.4 Test Product Preparation / Application:*

Test Product Preparation will be performed as noted below unless otherwise requested by Sponsor.

*Step 1: ColActive Plus Collagen Matrix Dressing: cut with sterile scissors into a 25-millimeter diameter.*

*Step 2: 0.8mL of distilled water will be dispensed to saturate the test product.\**

*Step 3: Aliquot test product into a reservoir to allow for the UniTest PC device to be dipped into the test product.*

*Step 4: Use the UniTest PC device to apply the test product to the subject volar forearm skin.*

*\*Visual inspection will be done to confirm saturation of the dressing with distilled water and test product has transformed into a gel.*

*9.5 Test Sites:*

The test product ColActive Plus Collagen Matrix Dressing, Positive control and Negative control will be applied directly to the volar forearm skin of the subject. The sites will be a minimum of 2cm from each other to minimize cross contamination.

Positive Control:

Use the UniTest PC device and apply the histamine positive control to subjects volar forearm.

Negative Control:

Use the UniTest PC device and apply the saline with glycerin (bacteriostatic) negative control, to subjects volar forearm.

Test sites should be more than 5 cm from the wrist and 3 cm from the antecubital fossa and marked by numbers on the skin to identify the test article, negative control and positive control.

*9.6 Procedure:*

The test area will be cleaned with an alcohol pad. A series of marks will be made using a skin pen on the subjects' volar forearm.

An aliquot of the test article will be placed in a reservoir. The UniTest PC device will be dipped into the reservoir and then pricked into volar forearm skin of panelist/subject. A new skin prick device will be used for each prick and will be performed in identical order for each panelist/subject. The UniTest PC device will be pressed through the drop of allergen extract and held against the skin for at least 1 second. There will be equal pressure applied for each test. The epithelial layer of the skin will be penetrated without inducing bleeding. A new UniTest PC device will be utilized for each allergen.

Excess solution from drops will be blotted using a clean Kim-wipe tissue. A timer will be used, sites will be read at 15-20 minutes following application.

Positive and negative controls will be measured first. The negative control should exclude presence of an allergen reaction. The positive control should include presence of an allergen reaction. Both controls must show correct reaction in order to proceed with study.\*

\*Erythema present in the test site of the negative control: According to the consulting allergist, it is acceptable for the negative control to elicit an allergic response as long as the wheal diameter of the positive control exceeds the wheal size of the negative control by at least 3mm. This is to account for individuals who have sensitive skin.

The test sites will be visually evaluated for any reaction by an allergist. The allergist will be blinded to any previous scores the entire study. A trained ALS staff member will scribe for the allergist. Subjects will be brought into the same

sufficiently lit (fluorescent bulbs) room each visit. Subjects will be sitting and will be instructed to expose test site. Grading will be performed during daylight hours between 8am-5pm

The wheal of each test will be measured. A positive being a wheal of  $\geq 3$  mm. (Section 7. Experimental Techniques and Methods).

Subjects will be given a panelist instruction handout. Subjects will be dismissed with instructions to keep the test area dry and to not expose the test area to direct sunlight. Subjects will also be instructed not to wet, wipe, cleanse, or cover the test sites. Subjects will be instructed to notify clinical staff during the course of the study should they begin using any new medications, cease taking any medications or have any change in their medical condition. Subjects will be instructed to remain in the testing facility.

At approximately 6-hour ( $\pm 30$  minutes) following the skin prick, test sites will be evaluated by an allergist. The allergist will be blinded to any previous scores. Subjects will be brought into the same sufficiently lit (fluorescent bulbs) room each visit. Subjects will be sitting and will be instructed to expose test site. Grading will be performed during daylight hours between 8am-5pm.

Following the 6-hour grading, subject will be dismissed from the testing facility and instructed to return approximately 24-48 hours post-application. Subjects will also be instructed not to wet, wipe, cleanse, and cover the test sites.

At approximately 24-48 hours following the skin prick, test sites will be evaluated by the allergist. The allergist will be blinded to any previous scores. Subjects will be brought into the same sufficiently lit (fluorescent bulbs) room each visit. Subjects will be standing and will be instructed to expose test site. Grading will be performed during daylight hours between 8am-5pm.

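### Nothing masks the allergist to which site holds the product, and the first reading reveals it by elimination, so expectation bias cannot be ruled out for wheals near 3 mm

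*Combined protocol and SAP*

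**What the plan says.** Section 7 describes a single-centre study "with no randomization or blinding". Each subject receives three pricks on the volar forearm: product, histamine control and saline-glycerin control.

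- **Prick order (9.6):** the pricks "will be performed in identical order for each panelist/subject".
- **Site marking (9.5):** the sites are "marked by numbers on the skin to identify the test article, negative control and positive control". No site map is given, and the documents do not say who holds the link between number and article.
- **Reading order (9.6, 15-20 minutes):** "Positive and negative controls will be measured first". This is not repeated for the 6-hour or the 24-48-hour reading.
- **Masking (9.6):** "The allergist will be blinded to any previous scores the entire study". The same masking to previous scores is stated again for the two later readings. No masking to site identity appears anywhere.
- **Decision rule (7):** the product is positive when its wheal reaches 3 mm "in response to the test product with expected reactions to both the positive and negative controls". Wheals are measured with a millimetre ruler, and small ones are confirmed by palpation.
- **Analysis (14):** individual responses are tabulated, and Section 14 states that there will be no statistical analysis.

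**The concern.** Whether a small wheal is present, and where its edge lies, are matters of reader judgement. By masking the allergist to earlier scores, the plan accepts that what a reader already knows can affect a reading. Knowing which site carries the product is the same kind of knowledge, and it is left open.

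The error could go either way. A reader expecting no reaction may call a borderline product wheal just under 3 mm, and one looking for a reaction may call it just over. A tendency common to all subjects does not shrink as subjects are added, and a table of individual responses cannot reveal it. Because the objective is sensitization potential, missed positives are the more worrying direction.

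**Working it through.** The plan has no figure of its own on this point to reproduce. Its n = 20 enters below only as the number of completers.

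**1. Is site identity masked?** The provisions that bear on it, side by side:
- Section 7: the design has no blinding.
- Section 9.5: skin numbers serve to identify the articles.
- Section 9.6, all three readings: the allergist is masked to previous scores only.

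None of these withholds site identity from the allergist.

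**2. What does the first reading reveal?** Three sites less two controls already measured leaves 1 site, which is the product. This holds at 15-20 minutes. For the later readings it depends on memory, or on access to the number key.

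**3. What does varying the layout change?** With one layout for everyone, learning it in one subject gives it for all. Three articles can be arranged in 3 x 2 x 1 = 6 orders, and 30 / 6 = 5 subjects per order. Suppose the histamine site is recognisable (assumption). For each of its 3 positions, 6 / 3 = 2 orders remain, equally frequent. An unaided guess between product and negative control is then right 1 time in 2.

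**4. Where can the bias act?** The product result is a per-subject classification at 3 mm. A shift matters only if it carries a product wheal across 3 mm, or alters the check that the positive control exceeds the negative by 3 mm.

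**5. How large could it be?** The documents give no wheal mean, SD or reader shift for a non-reactive site, so everything here is assumed. I take positive as at least 3 mm, as in Section 9.6; Section 7 also has a strict form, which is a separate matter.

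Upward shift: p = 1 - Phi((3 - mean - shift)/SD), and the chance of at least one false positive in 20 is 1 - (1 - p)^20.
- Mean 1.0 mm, SD 1.0 mm, shift 0 / 0.5 / 1.0 mm: p = 0.0228 / 0.0668 / 0.1587; expected false positives 20p = 0.46 / 1.34 / 3.17; chance of at least one = 0.369 / 0.749 / 0.968.
- Mean 0.5 mm, SD 0.75 mm, same shifts: chance of at least one = 0.009 / 0.074 / 0.369.

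Under-calling: P(0 of 20 positive) = (1 - rate x fraction called)^20.
- True rate 10%, with 100% / 80% / 60% of positives called: 12.2% / 18.9% / 29.0%.
- True rate 5%: 35.8% / 44.2% / 54.4%.

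The spread from 1% to 97% shows how little can be said about size. In the first upward scenario the chance is already 37% with no shift at all, so the assumed distribution drives much of the figure. That normal model also places Phi(-1) = 16% of wheals below 0 mm. These numbers show direction and sensitivity. They do not estimate the bias in this study.

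**The case against.** The best reply is that the study is openly declared to be unblinded, that ruler measurement and masking to earlier scores already limit reader influence, and that nothing in the documents shows a reader effect of any size. All of that is true, and it keeps this point modest. It does not close it: declaring the design open discloses the weakness without giving a reason for it, and a remedy is available within the planned procedures.

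Three stronger readings are tempting, and the documents do not support them.

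- **A reader might infer that the allergist knows the product site at every reading.** This is a reasonable inference, but it is not stated. The holder of the number key is not named, and the controls-first instruction appears only for the first reading.
- **A reader might infer that each article always sits at the same place on the forearm, so that position is confounded with article.** The fixed order concerns the sequence of pricks, and no site map is given.
- **A reader might infer that order and expectation cannot be separated from the product effect.** In a model with subject, article and order terms for 20 subjects (20 + 2 + 2 = 24 columns), a fixed order gives rank 22, and using all six orders gives rank 24. The aliasing is real algebra, but the plan fits no such model and estimates no product-minus-control effect. Each product wheal is compared with an absolute cut-off.

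For the same reason, rotating sites without masking would only spread any position effect over the three articles; a product site in a more reactive position could still cross 3 mm. The main value of varying the layout is that it cannot be learned. The scribe should not be cited as evidence that the plan is worried about reader bias, since Section 9.6 gives no such purpose.

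**Conclusion.** The point holds as a low-cost improvement. The plan fixes one prick order, numbers the sites to identify the articles, reads the controls first at 15-20 minutes, and masks the allergist only to previous scores. Site identity is therefore unprotected, and at the first reading it can be deduced. Expectation bias cannot be ruled out for wheals near 3 mm, in either direction.

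Its size is unknown, and the illustrative figures rest wholly on assumed means, SDs, shifts and calling fractions. Product wheals well clear of 3 mm are little affected, provided the control check also stands. The documents do not show that bias will occur, or that the study's result would be invalid.

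**What to change.** - **Section 9.6, prick order:** replace the fixed order with a prepared list that varies the order and site of product, positive and negative control across subjects: six orders, 5 subjects each at 30 enrolled. Exact balance among completers is not needed, because the purpose is that the layout cannot be learned.
- **Section 9.5, marking:** number the sites 1 to 3 by position only.
- **Pricks:** have existing trained staff other than the reading allergist perform them.
- **Key:** hold it on the case report form, out of the allergist's sight and not disclosed during reading. The scribe records wheals by site number.
- **Reading:** at all three time points, read sites 1, 2, 3 in numerical order. Apply the existing control-validity rule to the recorded wheals before the product result is accepted. All three pricks have been made by the first reading, so nothing is lost by checking the controls just after measurement instead of before.

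The cost is a wording change and a one-page list, with no extra pricks or visits. The downsides are a small risk of site mix-up, and masking that is only partial if the histamine site is recognisable (assumption). The documents do not say who does the pricks, so the sponsor must confirm that existing staff other than the allergist can do them.

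If the change is not made, the report should state that the readings were unmasked to site identity.

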## 10. SUBJECT DISCONTINUATION

The removal of a study subject by the Principal Investigator could occur due to the following reasons:

1. Adverse Event
2. Concomitant treatments or illnesses incompatible with the study
3. Withdrawal of consent by the participant
  - a. All subjects will be informed of the fact that they may, of their own free will, withdraw their consent to participate in the study, if they so wish.
4. Lost to follow-up
5. Emergence of a non-inclusion criterion
6. Researchers' decision
7. Protocol violation

Those subjects who, for some reason, are discontinued from the study will not be replaced. Data from these subjects will not be analyzed unless the reason for their discontinuation was related to the investigational product.

The Investigator should carefully track and document all premature discontinuations and the reasons on study documentation and also, when necessary, on the "adverse event" form.

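### A product wheal cannot be called positive when the histamine control fails, and the plan does not say how such a wheal is reported

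*Combined protocol and SAP*

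**What the plan says.** All references are to the combined protocol and SAP.

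- **Section 9.6 (Procedure).** Product, histamine and saline are all pricked before any site is read. At the first reading, "Positive and negative controls will be measured first", followed by the condition "Both controls must show correct reaction in order to proceed with study".
- **Section 7.** The histamine criterion is a margin: "The wheal at the positive control must exceed a wheal at the negative control by 3 mm". A product site with a wheal of at least 3 mm is positive only "with expected reactions to both the positive and negative controls, the site will be considered a positive allergen".
- **Sections 9.6 and 14.** The one relaxation concerns a reacting negative control. Such a subject "will be included as long as the wheal diameter of the positive control exceeds the wheal size of the negative control by at least 3mm". Nothing comparable is written for a weak histamine site with clean saline.
- **Section 10.** Discontinued subjects are not replaced, and "Data from these subjects will not be analyzed unless the reason for their discontinuation was related to the investigational product". Control failure is not named among the reasons for discontinuation.

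Sections 7 and 9.6 also state positivity by wheal size alone, without the control condition. Section 14 promises a table of product and control responses for each subject.

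**The concern.** The two controls guard against different errors, but Section 7 gives them the same power over a positive call. The plan's own account supports the distinction. Section 8 describes the wheal as the result of mast-cell release of histamine and other mediators. Section 5.2 excludes antihistamine users because such drugs could mask or disturb the result. A weak histamine wheal with clean saline therefore suggests suppressed reactivity or a poor control prick. Either makes a negative product reading unreliable. Neither, taken alone, produces a product wheal. A reacting saline site is different, because it does cast doubt on a positive.

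The objective in Section 2 is to detect sensitization, so a qualifying product wheal is the observation that the study exists to find. At stake is whether such a wheal appears in the reported count, appears only in a listing, or is left out. The plan does not settle which.

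**Working it through.** **Inputs.** Product threshold 3 mm and histamine-minus-saline margin of at least 3 mm (Sections 7, 9.6, 14); about 30 enrolled for 20 completers (Sections 5, 7). The documents give no control-failure rate, so there is no planned figure to reproduce. The n = 20 in Section 14 is taken as given, and the point does not depend on how it was derived.

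**Step 1: apply the Section 7 rule.** Positive = product wheal ≥ 3 mm and (histamine − saline) ≥ 3 mm. The diameters are illustrative.

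| Product (mm) | Histamine (mm) | Saline (mm) | Margin (mm) | Controls met | Section 7 positive |
|---|---|---|---|---|---|
| 5 | 6 | 0 | 6 | yes | yes |
| 5 | 6 | 3 | 3 | yes | yes |
| 5 | 2 | 0 | 2 | no | no |
| 3 | 0 | 0 | 0 | no | no |
| 5 | 5 | 3 | 2 | no | no |
| 0 | 2 | 0 | 2 | no | no |

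Rows 3 and 4 are the problem: the product wheal meets the size threshold and saline is clean, yet no positive call is allowed. In row 5 the margin fails because saline reacted, so withholding a positive is defensible. In row 6 the negative is unreliable, so setting it aside is right.

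**Step 2: effect of one uncounted wheal.** Suppose 20 subjects with valid controls show no product wheal, and one further subject is as in row 3.

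- Not counted: 0/20 = 0%. Exact two-sided 95% upper limit = 1 − 0.025^(1/20) = 16.8%.
- Counted: 1/21 = 4.8%, exact 95% CI 0.1–23.8%.

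**Step 3: effect on the denominator.** The gate does not depend on the product result, so it also removes negatives. Suppose 4 of 20 subjects are product-negative with failed histamine.

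- One valid positive among the rest: 1/20 = 5.0% without the gate, 1/16 = 6.3% with it.
- No positives: the upper limit goes from 16.8% (0/20) to 1 − 0.025^(1/16) = 20.6% (0/16).

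Removing these negatives is appropriate and works against a reassuring result.

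**Step 4: how often it might arise.** With an assumed control-failure rate f, the chance of at least one failure among 30 subjects is 1 − (1 − f)^30: 45% at f = 2%, 79% at 5%, 96% at 10%. These rates are assumptions. The event of interest also needs a product wheal in the same subject, so it is rarer by an amount that the documents do not allow one to estimate. The planned gap of 30 − 20 = 10 subjects (33%) covers loss for any reason and is not a control-failure rate.

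**The case against.** The strongest reply is that the plan may already capture the wheal. Reading the controls first is an order, not a stop. Section 9.6 also has every test's wheal measured, Section 7 has all three sites read at the first time point, and Section 14 tabulates each subject. Proceeding with the study is undefined and could refer only to the later readings. This stands. A reader might infer that the product reaction would go unmeasured, but the documents do not say so. Nor do they say that control failure is a discontinuation, so loss under Section 10 is a possibility and not a stated rule. Section 11 separately requires adverse events to be recorded and followed up.

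A second reply is that a 5 mm product wheal beside a 2 mm histamine wheal could mean swapped sites or reagents, since sites are identified by numbers marked on the skin and devices are dipped in reservoirs. This also stands, and is a reason to flag the result and check for a mix-up before relying on it. It is not a reason to leave the result without a category.

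A third reply is that the event is unlikely, because antihistamine users and people with known fish allergy are excluded. That is accepted.

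None of these replies removes the conditional definition in Section 7, which still bars the positive call even when the wheal is measured and listed.

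**Conclusion.** The point holds, limited to uncounted positives: a product wheal meeting the threshold, with saline clean and the histamine margin not met, cannot be called positive under Section 7, and no section says how to report it. In the illustration, one such wheal moves the reported count from 0/20 to 1/21. That rests on an assumed event of unknown and probably low frequency.

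Two stronger conclusions are tempting and are not supported. A reader might infer that the gate always favours a finding of no sensitization; Step 3 shows that it also removes negatives, which can raise the reported rate and its upper limit. A reader might also infer that one wheal would reverse the study's conclusion. The documents set no rule by which the absence of reactions leads to a conclusion, and the two intervals in Step 2 overlap almost entirely. What changes is the count, and whether the report says that no positive was seen.

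This is an inexpensive improvement in classification and reporting. It does not show that the study is invalid.

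**What to change.** 1. **Section 9.6.** State that the 15–20 minute product measurement is taken and recorded in every pricked subject, whatever the controls show. Reconcile this with the sentence on proceeding, and say what that sentence governs.
2. **Section 7.** Require a histamine margin of at least 3 mm over saline for a negative call. When histamine fails and the product wheal meets the threshold and exceeds saline, report it in a separate category, *product wheal, histamine control not met*, neither counted as negative nor dropped. Record the check for a site or reagent mix-up. Reconcile the size-only statements of positivity in Sections 7 and 9.6 with this rule.
3. **Sections 10 and 14.** List every control-failure subject with all three wheal diameters, so that failures caused by a reacting saline site can be told apart. Exempt these subjects from the Section 10 exclusion of data. Give the count of positives with and without the flagged category.

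The cost is at most one extra ruler measurement in the few control failures, one more category in the table, and a few flagged results to explain in the report.
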